5.3.3 Efficacy

5.3.3.1 General

Participants who used permitted rescue therapy less than 28 days before Week 16 or discontinued study due to treatment related reason should be considered as non-responder in the primary estimand for the primary endpoint.

5.3.3.2 Eczema Area and Severity Index (EASI)

The Eczema Area and Severity Index (EASI) will be calculated within the [REDACTED] system and taken directly from the supplied data. EASI score ranges from 0 to 72. Further information on the scoring of the EASI is provided in [Section 16](#).

EASI -50, EASI -75 and EASI -90 responses are defined respectively by at least a 50%, 75% and 90% decrease from Baseline in the EASI score.

Sustained EASI-50 response is defined as one which is present on at least two consecutive visits. The sustained response is considered to have been first achieved at the first of the consecutive visits.

5.3.3.3 The Percent of Body Surface Area Involvement (BSA)

The Body Surface Area (BSA) will be calculated as part of EASI score in the [REDACTED] system and taken directly from the supplied data. The percent of BSA involvement will be estimated for each participant, where 1% is approximately the area of the participant's handprint.

BSA-50 and BSA-75 responses are defined respectively by at least a 50% and 75% reduction from Baseline in the BSA.

5.3.3.4 Validated Investigator's Global Assessment (vIGA)

The Validated Investigator Global Assessment scale for Atopic Dermatitis (vIGA) will be calculated within the [REDACTED] system and taken directly from the supplied data. There is a standardised grading system based on an overall assessment of the degree of erythema, papulation/induration, lichenification, and oozing/crusting. In indeterminate cases, extent will be used to differentiate between scores - but otherwise extent is not used in the scoring system. The vIGA score ranges from 0 to 4.

5.3.3.5 SCORing Atopic Dermatitis (SCORAD)

The SCORing Atopic Dermatitis (SCORAD) will be calculated within the [REDACTED] system and taken directly from the supplied data. There is an investigator-rated area score which uses the rule of

nines to assess disease extent, and a disease intensity score comprising erythema, swelling, oozing/crusting, excoriation, lichenification, and dryness. Additionally, there is a subjective symptoms component which considers itch and sleeplessness scored using a visual analogue scale. These scores combine to give a SCORAD score between 0 and 103.

SCORAD-35, SCORAD-50 and SCORAD-75 responses are defined respectively by at least a 35%, 50% and 75% reduction from Baseline in the SCORAD score.

5.3.3.6 Patient Oriented Eczema Measure (POEM)

The Patient Oriented Eczema Measure (POEM) will be calculated within the [REDACTED] system and taken directly from the supplied data. It includes a series of 7 questions, measuring itch, sleep, bleeding, weeping/oozing, cracking, flaking, and dryness/roughness over the last week, and is scored by the participant. Each of the 7 questions is scored from 0 (no days) to 4 (every day), giving a POEM score range from 0 to 28, with higher scores representing higher disease severity.

POEM response is defined as a reduction of ≥ 4 in the POEM score if a participant has a score of ≥ 4 at baseline.

5.3.3.7 Dermatology Life Quality Index (DLQI)

The DLQI is a 10-item questionnaire with each item scored from 0 to 3.

The DLQI score is the sum of the 10 individual items and ranges from 0 to 30, with higher scores indicating greater impairment of quality of life. Further information on the scoring of the DLQI is provided in [Section 20](#).

DLQI response is defined as a reduction of ≥ 4 in the DLQI score if a participant has a score of ≥ 4 at baseline (a 4-point change from baseline is considered the minimal clinically important difference threshold).

5.3.3.8 Peak Pruritus Numerical Rating Scale (PP-NRS)

The Peak Pruritus Numerical Rating Scale (PP-NRS) is a scale from 0 to 10 for participants to rate their worst itch that they have experienced over the previous 24 hours. The PP-NRS will be completed as a part of daily symptom diary from the Screening Visit to end of study.

PP-NRS score at each visit is calculated as the mean itch daily score for the 7 days prior to and including the visit date. At least 4 daily scores must be available for the score at the relevant visit to be considered evaluable.

PP-NRS responses are defined as a reduction of ≥ 2 and ≥ 4 in the PP-NRS score if a participant has a score of ≥ 2 and ≥ 4 , respectively, at baseline (a ≥ 2 -4-point change from baseline is considered the minimal clinically important difference threshold).

Sustained PP-NRS response is defined as one which is present at all available assessments within at least 14 days period. Sustained response is considered to have been first achieved at the first of the consecutive days.

5.3.3.9 Sleep Disturbance Numerical Rating Scale (SD-NRS)

The Sleep Disturbance Numerical Rating Scale (SD-NRS) is a scale from 0 to 10 for participants to rate their worst sleep that they have experienced over the previous 24 hours. The SD-NRS will be completed as a part of daily symptom diary from the Screening Visit to end of study.

SD-NRS score at each visit is calculated as the mean sleep daily score for the 7 days prior to and including the visit date. At least 4 daily scores must be available for the score at the relevant visit to be considered evaluable.

SD-NRS response is defined as a reduction of ≥ 2 in the SD-NRS score if a participant has a score of ≥ 2 at baseline (a 2-point change from baseline is considered the minimal clinically important difference threshold).

Sustained SD-NRS response is defined as one which is present at all available assessments within at least 14 days period. Sustained response is considered to have been first achieved at the first of the consecutive days.

5.3.3.10 Time to First Achievement of Daily Time-to-Event Endpoints

The daily time-to-event endpoints are based on a daily questionnaire and include:

- Time to first achievement of a ≥ 2 point in improvement in PP-NRS score, in participants with a score of ≥ 2 at baseline
- Time to first achievement of a sustained ≥ 2 point in improvement in PP-NRS score, in participants with a score of ≥ 2 at baseline
- Time to first achievement of a ≥ 4 point in improvement in PP-NRS score, in participants with a score of ≥ 4 at baseline
- Time to first achievement of a sustained ≥ 4 point in improvement in PP-NRS score, in participants with a score of ≥ 4 at baseline
- Time to first achievement of a ≥ 2 point in improvement in SD-NRS score, in participants with a score of ≥ 2 at baseline
- Time to first achievement of a sustained ≥ 2 point in improvement in SD-NRS score, in participants with a score of ≥ 2 at baseline

Time to event is defined as the time in days from the first dose of study drug until the date when event occurred.

Participants who complete the study up to Week 16 visit without experiencing the relevant event will be censored on the date of Week 16 visit. Participants who prematurely withdraw from the study before Week 16 without experiencing the relevant event will be censored on the date of treatment discontinuation.

For sustained response endpoints censoring rules are adjusted to consider that sustained response cannot be achieved less than 14 days before the end of the relevant period. Therefore, participants who complete 16 weeks of study or prematurely withdraw from the study without experiencing the relevant event will be censored 14 days before the date of Week 16 visit/withdrawal, if before Week 16.

Time to the relevant event will be calculated as:

$$\text{Time to event (days)} = \text{Date of event/censoring} - \text{date of the first study drug (Day 1)} + 1$$

5.3.3.11 12-Item Short Form Health Survey (SF-12)

The 12-Item Short Form Health Survey (SF-12) is a PRO instrument consisting of twelve questions used to measure non-disease related outcomes in 8 health domains, including vitality, physical functioning, bodily pain, general health perceptions, physical role functioning, emotional role functioning, social functioning, and mental health. The score (ranging from 0 to 100) is presented in two components: a mental composite scale (MCS) and physical composite scale (PCS). The higher the score, the better the physical and mental health functioning.

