11.4.5. Analysis of Exploratory Estimands

Exploratory endpoints will be summarized only. No inferential analysis is planned.

For the daily PP-NRS and SD-NRS endpoints which are evaluated daily only graphical summaries will be presented.

For the time to first response endpoints for the PP-NRS and SD-NRS scores, participants who have not met the response definition before the Week 16 visit will be censored at the Week 16 visit, or at the time of withdrawal from the study for those who withdrew before Week 16.

For the time to sustained response endpoints for the PP-NRS and SD-NRS scores, it will not be possible for participants to start a sustained response less than two weeks before the Week 16 visit. Therefore, such participants will be censored at 14 days before the date of the Week 16 visit or at the time of treatment withdrawal for participants who do not complete the 16-week treatment period.

For the primary and secondary responder endpoints relating to EASI, IGA and BSA, summaries will be provided comparing the number and percentage of participants in each treatment group who respond at Week 16 between the following 4 subgroups:

- Participants with no rescue therapy use
- Participants with no rescue therapy use after the Week 4 visit
- Participants with no rescue therapy use after the Week 8 visit
- Participants with no rescue therapy use within 4 weeks of the Week 16 visit
- Participants with no rescue therapy use within 2 weeks of the Week 16 visit
- Participants with rescue therapy use within 4 weeks of the Week 16 visit
- Participants with rescue therapy use within 2 weeks of the Week 16 visit

For these endpoints, all participants who have Week 16 data available for the relevant endpoint will be included and there will be no imputation for any intercurrent events.

For the Cohorts 1-3 analyses, pairwise treatment differences between two EDP1815 treatment groups will be estimated as part of the modelling done for the primary and secondary analyses, but such estimates will be considered as exploratory.

For the Cohort 4 analyses of the primary and selected secondary estimands, separate models will be used which include the EDP1815 1.6x10¹¹ (Cohort 1) treatment group in addition to the Cohort 4 EDP1815 8.0x10¹⁰ group and the Cohort 4 Matched Placebo group. From these tables, pairwise treatment differences between the two active EDP1815 groups will be estimated, with all such estimates being considered as exploratory.

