7.1.2.1 Efficacy Data Point Set 1 (EDPS1)

EDPS1 consists of all data collected at a scheduled timepoint that is at least 28 days after use of TCS/TCI rescue therapy* or type 1 prohibited medication and before use of type 2 prohibited medication. Data collected less than 28 days after such use or data missing due to withdrawal from the study for reasons considered related to study medication** or data collected after use of type 2 prohibited medications will be replaced as follows:

- Continuous endpoints: value will be imputed with the last off-rescue¹ observation in the period before the event plus early termination visit in case of early study discontinuation (off-rescue is defined as data collected at least 28 days after use of rescue medication or type 1 prohibited medication)
- Responder endpoints: value will be imputed as non-response.
- Count endpoints: N/A (no count endpoint will use this DPS).

Data missing for other reasons, including early withdrawal from the study due to reasons not considered related to study medication will not be replaced and will be considered as missing.

Example 1: if patient completed 16 weeks of study with rescue therapy during week 3 and then during week 10 then responder endpoints will be analysed as shown in table:

Week 0	Week 2	Week 4	Week 8	Week 12	Week 16
As collected	As collected	Imputed as non-responder because there was a rescue therapy within 28 days before Week 4 visit	As collected	Imputed as non-responder because there was a rescue therapy within 28 days before Week 12 visit	As collected

Example 2: if patient completed 16 weeks of study with rescue therapy from Day 25 to Day 31 then responder endpoints will be analysed as shown in table:

Week 0	Week 2	Week 4	Week 8	Week 12	Week 16
As collected	As collected	Imputed as non-responder because there was a rescue therapy within 28 days before Week 4 visit	Imputed as non-responder because there was a rescue therapy within 28 days before Week 4 visit	As collected	As collected

Example 3: if patient withdrew study early due to the lack of efficacy after 12 weeks of treatment with rescue therapy during week 3 (unscheduled rescue therapy visit was not done) and then during week 10 (unscheduled rescue therapy visit was done at Week 9 prior to the rescue therapy start) then continuous endpoints will be analysed as shown in table:

Week 0	Week 2	Week 4	Week 8	Week 12	Week 16

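### Time to first itch or sleep response: Week 16 completers are censored at the clinic visit, not at their last diary entry, so days without diary data count as observed non-response

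*SAP*

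**What the plan says.** SAP 5.3.3.10 covers six endpoints. Three are times to first achievement (PP-NRS improvement of at least 2 points, PP-NRS of at least 4, SD-NRS of at least 2) and three are the sustained versions of these. It introduces them as follows: "The daily time-to-event endpoints are based on a daily questionnaire and include".

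Censoring of participants without an event:

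- **First achievement, Week 16 completers.** They are followed to the clinic visit: those who complete "without experiencing the relevant event will be censored on the date of Week 16 visit". Protocol 11.4.5 agrees: "participants who have not met the response definition before the Week 16 visit will be censored at the Week 16 visit".
- **First achievement, early withdrawals.** In the SAP they "will be censored on the date of treatment discontinuation". Protocol 11.4.5 uses the time of withdrawal from the study.
- **Sustained response.** Participants "will be censored 14 days before the date of Week 16 visit/withdrawal, if before Week 16". The SAP's reason is that a sustained response cannot be reached in the last 14 days of the period.

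SAP 5.3.3.8 defines the sustained endpoint on the entries that exist: "Sustained PP-NRS response is defined as one which is present at all available assessments within at least 14 days period". Section 5.3.3.9 does the same for SD-NRS. For visit-level scores, by contrast, the SAP sets a completeness rule: "At least 4 daily scores must be available for the score at the relevant visit to be considered evaluable".

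SAP 9.5.1 and the table list in Appendix 1 assign EDPS1 to all six endpoints. SAP 7.1.2.1 says of EDPS1: "Data missing for other reasons, including early withdrawal from the study due to reasons not considered related to study medication will not be replaced". SAP 9.5.1.2 reports Kaplan-Meier proportions by week (to Week 16 for first achievement, to Week 14 for sustained) and, for first achievement, the median and quartiles.

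**The concern.** Censoring should fall where observation of the event ends. Here observation ends with the last diary entry, but the rule uses a clinic date that does not depend on the diary. A completer whose entries end on Day 30 without a response remains in the risk set until the Week 16 visit, scheduled for Day 113. That is 113 − 30 = 83 days counted as follow-up without response.

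This is not a declared composite strategy. EDPS1 sets responder data to non-response for TCS/TCI rescue or type 1 prohibited medication within 28 days, for type 2 prohibited medication, and for data missing after treatment-related withdrawal. A lapsed diary is none of these. The SAP also already applies the right principle to the sustained endpoints, where it moves the censoring date back because the event could not occur in the remaining time.

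At stake is the diary-based description of time to onset, the first exploratory objective. Weekly response proportions would be too low, and the median and quartiles too late.

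**Working it through.** The plan states no figure for this point, so there is none to reproduce. The check asks how far the rule moves the Week 16 Kaplan-Meier proportion for first achievement.

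**Inputs**

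- From the documents: censoring at the Week 16 visit, events seen only on diary days, 112 days of treatment.
- Assumed, because the documents give no diary drop-off rate: true Week 16 response p of 30%, 50% or 70%; a share f of Week 16 attenders stops the diary for good, at a time uniform over 112 days and unrelated to response; constant response hazard. Withdrawals are left out.

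**Formula.** If every non-event is censored at Week 16, nobody leaves the risk set earlier except by responding. The Kaplan-Meier estimate is then the share of participants whose response was seen:

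estimate = (1 − f)·p + f·q

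Here q is the chance that a stopper responds before stopping. With a = −ln(1 − p), the cumulative hazard over 112 days, q = 1 − p/a.

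**Numbers for p = 50%.** a = 0.6931, so q = 1 − 0.5/0.6931 = 0.2787.

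- f = 20%: 0.8 × 0.5 + 0.2 × 0.2787 = 45.6%
- f = 30%: 0.7 × 0.5 + 0.3 × 0.2787 = 43.4%
- f = 40%: 0.6 × 0.5 + 0.4 × 0.2787 = 41.1%

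The same formula for the other response rates:

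| True response | q | f = 0 | f = 20% | f = 40% |
|---|---|---|---|---|
| 30% | 0.1589 | 30% | 27.2% | 24.4% |
| 50% | 0.2787 | 50% | 45.6% | 41.1% |
| 70% | 0.4186 | 70% | 64.4% | 58.7% |

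A Kaplan-Meier simulation with 40,000 participants per scenario agrees within 0.6 percentage points (45.6% and 41.0% for p = 50%). In the same data, censoring at the last diary entry gives 49.8% to 50.1% for p = 50%.

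**Earlier responses.** Replace the constant hazard by a front-loaded one (Weibull, shape 0.5, also an assumption). Then q = 1 − 2[1 − (1 + a)e^(−a)]/a². For p = 50% this is 0.3613, and the estimates are 47.2% at f = 20% and 44.5% at f = 40%.

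**Sustained endpoints.** These were simulated with 4,000 participants and autocorrelated daily scores; the scenario is illustrative.

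| Stop early | True | Full 14-day window required, censored at Week 16 − 14 days | All available entries, read literally |
|---|---|---|---|
| 20% | 11.8% | 9.9% | 12.6% |
| 40% | 11.3% | 7.9% | 13.3% |

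With a full window required, late censoring understates response. Under the literal wording, a short run of good entries just before the diary stops counts as a 14-day response, and the estimate is too high.

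**The case against.** Five points can be made for the plan as written.

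- **The rule is conservative, and the alternative has its own assumption.** Last-entry censoring is unbiased only if stopping is unrelated to later response. Take a true 50%, a constant hazard, and stoppers who are all true non-responders stopping at uniform times. The visit rule then returns 50%. Last-entry censoring tends to 1 − exp(−∫ a·e^(−au)/(e^(−au) − f·u) du), with u from 0 to 1, which is 57%, 62% and 70% at f = 20%, 30% and 40%. This is an extreme case and does not make unobserved days into observed ones, but it belongs in the stated cost of the fix.
- **EDPS1 does count some unusable time as non-response.** That is true for rescue, prohibited medication and related withdrawal, and the fix must leave it alone. It does not reach a diary that simply lapses.
- **Drop-off may be small.** Staff review the eDiary at each visit and coach participants (Protocol 6.6.1). This stands. The bias needs permanent stopping before any response by people who still attend Week 16.
- **Noisy daily scores may cross a threshold early.** This stands, and it shrinks the figures as shown. For that reason no fixed drop-off rate can be named at which the bias becomes material.
- **The endpoints are descriptive.** Protocol 11.4.5 plans no inferential analysis of them. This stands.

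A reader might also infer that the rule creates a false difference between arms because improved participants stop reporting. That does not work for first achievement: their improvement is normally already recorded as an event. Unequal drop-off before response would matter (20% against 40% at the same true 50% reads as 45.6% against 41.1%), but nothing in the documents suggests that drop-off differs by arm.

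**Conclusion.** The point holds for the three first-achievement endpoints. The censoring date is not tied to diary observation, it conflicts with EDPS1's handling of data missing for other reasons, and it understates the Kaplan-Meier response. Under a constant hazard and uniform, non-informative stopping by 10% to 40% of completers, the understatement is about 1 to 11 percentage points for true responses of 30% to 70%. It is smaller if responses come early and zero if nobody stops. The drop-off rate is an assumption throughout.

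A reader might extend the understatement to all six daily endpoints. The documents do not support that: the sustained definition uses whatever entries are available, with no minimum number, so the error can go either way. Nor does the point touch the primary analysis, its power, or the visit-level PP-NRS and SD-NRS secondary endpoints, which have their own completeness rule. This is a low-priority correction to descriptive outputs.

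**What to change.** In SAP 5.3.3.10:

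- **First achievement.** Where diary data are missing for reasons that EDPS1 leaves as missing, censor participants without an event at the last non-missing PP-NRS or SD-NRS entry on or before the Week 16 visit, or at the existing withdrawal censoring date if that is earlier. Keep EDPS1's composite non-response for rescue, prohibited medication and related withdrawal unchanged.
- **Sustained response.** Censor at the last day that can start an evaluable 14-day window, and state the minimum number of entries a window needs.
- **Withdrawals.** In the same edit, reconcile the SAP's treatment-discontinuation date with the protocol's study-withdrawal date.

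The cost is a few sentences and a changed censoring date in the programming. Late Kaplan-Meier intervals will be slightly wider. The estimate will rest on stopping being unrelated to later response and will be too high if people who are not improving stop. Keeping the Week 16 visit censoring as a sensitivity display would show how much depends on that assumption.

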5.3.3.12 Hospital Anxiety and Depression Scale (HADS)

The Hospital Anxiety and Depression Scale (HADS) is a PRO instrument used to measure anxiety and depression over the past week. It is comprised of 7 questions for anxiety and 7 questions for depression and each are scored using a 4-point Likert scale (e.g., 0-3). Scores for each domain therefore, range from 0-21, where 8-10 is mild, 11-14 is moderate and 15-21 is severe anxiety or depression.

5.3.3.13 Atopic Dermatitis Control Tool (ADCT)

The Atopic Dermatitis Control Tool (ADCT) is a 6-question PRO instrument used to detect change of disease activity in a person over time. There are six main areas that assess the multi-dimensional aspects of disease control over the course of a week, scored between 0-4. ADCT scores range from a minimum score of 0 and a maximum score of 24. A higher score indicates lower AD control.

5.3.3.14 Rescue Therapy

Rescue therapy use is allowed throughout the entire study: selected topical corticosteroids and calcineurin inhibitors systemic antimicrobials and topical antibacterial may be prescribed. An unscheduled visit will be performed to collect skin assessments prior to administering any rescue therapy, if needed.

Rescue therapy use will be documented as concomitant medication once prescribed and in a daily symptom diary during the whole course. Each rescue therapy course will be recorded in concomitant medication CRF separately, resulting in a one record in a concomitant medication dataset for each course.

Any medications taken during the study and classified as TCS/TCl rescue therapy medications in the sponsor provided spreadsheet with total course duration no more than 8 days (adjusted for dosing

frequency – only days with planned medication usage are counted in course duration) will be considered as rescue therapy with exception for medications which stopped at least 14 days before Day 1 – these cannot be rescue therapy.

For the number of courses of TCS/TCI rescue therapy in Weeks 1-4, 5-8, 9-12, 13-16, course will only be counted at the start day of course. If the rescue therapy course starts in one period and continues to the next period it will be counted only in the first period where the start of the course belongs. The number of courses of rescue therapy will be also evaluated for the whole period of Weeks 1-16.

For the same periods, rescue therapy use will be evaluated. In case of rescue therapy course overlap with the period, the participant will be considered as those who used rescue therapy in this period.

The number of days requiring TCS/TCI rescue therapy in Weeks 1-8, 9-16, 1-16 will be calculated as:

Number of days requiring rescue therapy (days) = min(therapy stop date, the end of the period date) – max(therapy start date, the start of the period date) + 1

In case of multiple rescue therapy medications concurrently, the day still will be counted only once.

